### 6.6.2 Concomitant therapies

In case of (partially) missing start and end dates of concomitant therapies, the dates will be imputed so that the extent of exposure to the concomitant therapy is maximal, i.e. the first day (month) of the month (year) for incomplete start dates and the last day (month) of the month (year) for incomplete end dates.

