## **7. PLANNED ANALYSIS**

For End-Of-Text (EoT) tables, the set of summary statistics is: N / Mean / SD / Min / Median / Max.

Tabulations of frequencies for categorical data will include all possible categories and will display the number of observations in a category as well as the percentage (%) relative to the respective treatment group (unless otherwise specified, all patients in the respective patient set whether they have non-missing values or not). Percentages will be rounded to one decimal place. The category missing will be displayed only if there are actually missing values.

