### **7.2 CONCOMITANT DISEASES AND MEDICATION**

According to the CTP, there are fewer restrictions in concomitant therapies in 1199.33 as compared to parent trial. No comparison is therefore possible between parent and extension trial, even for placebo-randomized patients in parent trial.

Baseline therapies will be defined as treatments with a start date before first trial drug intake in extension trial and taken after or on the day of the first trial drug intake in extension trial.

On-treatment concomitant therapies are defined as treatments with a start date after or on the day of first trial drug intake in extension trial and before or on the day of last trial drug intake in extension trial.

A summary of all on-treatment concomitant therapies (including baseline CTs) will be provided by randomised treatment in parent trial, ATC3 codes and Preferred Name (PN) (sorted by alphabetical ATC class and decreasing frequency of preferred names within ATC class).

Post-study drug discontinuation therapies are defined as treatments started between last trial drug intake and the latest between trial completion and last drug intake + 28 days (included). They will be summarized by randomised treatment in parent trial, ATC3 codes and Preferred Name (PN). This aims at flagging concomitant treatments taken by patients after they have stopped the study drug.

Relevant groups of therapies have been defined as Special Search Categories (SSC) or Standardised Drug Groupings (SDG). These are listed in [Section 9.3](#).

The summary of all on-treatment concomitant therapies (baseline CTs and on-treatment CTs) will also be performed by Special Search Category (SSC) or Standardised Drug Groupings (SDG) and Preferred Name (PN) (sorted by alphabetical SSC or SDG and decreasing frequency of preferred names within SSC).

Only descriptive statistics are planned for this section of the report.

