## 10. HISTORY TABLE

This is a revised TSAP including the following modifications to the final TSAP

Table 10: 1 History table

Version	Date (DD-MMM-YY)	Author	Sections changed	Brief description of change
Final	14-June-13	[REDACTED]	None	This is the final TSAP without any modification
Revised	29-September-15	[REDACTED]	4	As the protocol has been revised, the term "On trial survival" has already been changed into "Time to death"
			5.2.2	In accordance with new SOP, endpoints are now classified as further endpoints and not as secondary endpoints anymore.
			[REDACTED]	[REDACTED]
			[REDACTED]	[REDACTED]
			[REDACTED]	[REDACTED]
			[REDACTED]	[REDACTED]
			6.2	Precision added for IPV A2.1
			6.6	A reference to the CTP has been added for the handling of missing data.
			7.5.2	In accordance with new SOP, endpoints are now classified as further endpoints and not as secondary endpoints anymore.
			[REDACTED]	[REDACTED]
			7.7, 7.8.1	Precision that KM plots will also be performed overall groups and with 70% cut-off for y-axis for AEs of particular note
			[REDACTED]	[REDACTED]
			General	Reference section numbers have been updated or removed due to new classification of endpoints and for consistency purposes with revised CTP based on Global amendment 2.

Table 10: 1 History table (cont'd)

Revised	19-September-16	[REDACTED]	6.3	The definition of the Treated Set has been updated in order to specify that the Treated Set only includes patients from parent trials 1199.32/34 (and not transitioned patients from study 1199.35).
				[REDACTED]
Revised	25-Jul-17	[REDACTED]	7.2	The definition of baseline therapies was clarified. A summary of post-study drug discontinuation therapies has been added in order to display the proportion of patients having taken commercial nintedanib after trial drug discontinuation.
			7.8	Some specific AE tables by Topic or syndrome were added, as judged medically relevant for the project.
				[REDACTED]
				[REDACTED]

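### Imputing partial start dates to the earliest day can move commercial nintedanib begun after the last trial dose out of the post-discontinuation summary and into the on-treatment table

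*SAP*

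**What the plan says.** SAP 6.6.2 covers missing and partly missing concomitant-therapy dates. Its aim is that "the dates will be imputed so that the extent of exposure to the concomitant therapy is maximal". For starts this means "the first day (month) of the month (year) for incomplete start dates".

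SAP 7.2 defines the classes that use those dates. An on-treatment therapy starts on or after the first trial dose and "before or on the day of last trial drug intake in extension trial". For the other class, "Post-study drug discontinuation therapies are defined as treatments started between last trial drug intake and the latest between trial completion" and 28 days after last intake, that day included. The on-treatment class has its own table: "A summary of all on-treatment concomitant therapies (including baseline CTs) will be provided by randomised treatment in parent trial".

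The SAP history table (Section 10, entry of 25 July 2017) says the post-discontinuation summary was added "in order to display the proportion of patients having taken commercial nintedanib after trial drug discontinuation".

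Neither SAP 6.6 nor protocol Section 7.5 contains a separate rule for a therapy begun around the end of trial treatment.

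**The concern.** A maximal-exposure rule is ordinary for background therapy, where the aim is not to miss concomitant use. It works against a summary whose purpose is to find drug started after the trial drug was stopped, because it pulls the start back across the boundary that the summary depends on.

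Commercial nintedanib is the therapy most exposed to this. The rationale for protocol Amendment 3 says the drug had become available outside the trial in most participating countries and that the trial would end there. A direct move from trial drug to commercial drug is therefore an expected exit, and a short gap is where the imputation does most damage.

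Two tables are at stake. The post-discontinuation summary can miss patients it was added to count. The on-treatment table can show nintedanib taken together with trial nintedanib when this did not happen.

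**Working it through.** The plan gives no figure on this point, so there is none to reproduce. The check applies the SAP 6.6.2 rule and the SAP 7.2 class boundaries to calendar dates.

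**Single case.** Last trial dose 15 June; commercial nintedanib truly started 20 June; recorded as June with no day. The imputed start is 1 June. Since 1 June is before 15 June, the record is on-treatment and not post-discontinuation. This is certain for every day-missing start in the month of the last dose. If the start falls in a later month, the 1st of that month is after the last dose and the class is correct. If the month is missing too, the same holds with year in place of month. An imputed date before the first trial dose makes the record a baseline therapy, which the on-treatment table also includes.

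**Share of partial records moved.** Assumptions not in the documents: the last dose is equally likely on any calendar day, and commercial drug starts g days later, with g from 1 to 28. A day-missing record is classified correctly only if a month boundary lies between dose and start, which happens for 12g of the 365 possible days:

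- day missing: share moved = 1 − 12g/365
- day and month missing: share moved = 1 − g/365

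| Gap g (days) | Day missing | Day and month missing |
|---|---|---|
| 1 | 1 − 12/365 = 97% | 99.7% |
| 7 | 1 − 84/365 = 77% | 98% |
| 14 | 1 − 168/365 = 54% | 96% |
| 21 | 1 − 252/365 = 31% | 94% |
| 28 | 1 − 336/365 = 8% | 92% |

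A day-by-day count over a two-year span gives the same percentages. With g uniform over 1 to 28 the mean gap is 14.5 days, and the average day-missing share is 1 − 12 × 14.5/365 = 52%. With g uniform over 1 to 7 it is 1 − 12 × 4/365 = 87%.

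**Undercount.** Let q be the fraction of commercial nintedanib starts with the day missing. The proportion of true starters lost from the summary is q × share moved:

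| q | g uniform 1–28 | g uniform 1–7 |
|---|---|---|
| 0 | 0 | 0 |
| 1% | 0.5% | 0.9% |
| 5% | 2.6% | 4.3% |
| 10% | 5.2% | 8.7% |
| 30% | 15.7% | 26% |

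**Opposite error.** Where the window ends at 28 days, a day-missing start just after it can be pulled in: 92% of such records at day 29, 77% at day 35, 54% at day 42. This needs a start recorded after the window has closed, which a follow-up visit at 28 (+7) days makes uncommon.

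**Boundary day.** A therapy started on the day of last intake meets the on-treatment definition. It can also be read as falling in the post-discontinuation window, because the text does not say whether that window's first day is included.

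**The case against.** The strongest reply is that the problem is conditional and may be small. Nothing in the documents says that any commercial nintedanib start date is partial. The protocol flow charts collect concomitant therapy at the End of Treatment and Follow-up visits, and protocol Section 8.2 provides for source verification. A drug started within about four weeks of the last dose should usually be recorded with its day, and a missing month is improbable. This stands. It limits the size but does not remove the misclassification when a partial date does occur.

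It is also fair that parts of the SAP, including Section 9.3 and some history rows, are not visible in the public text. Special handling there cannot be excluded.

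A reader might infer more in two places. The first is that the percentage is biased because SAP Section 7 by default divides by "all patients in the respective patient set whether they have non-missing values or not", which includes patients who died on drug or are still taking it. That default applies unless otherwise specified, and a percentage of the Treated Set is a valid description; it answers a different question from a percentage of those who stopped alive. The second is that the summary is needed to separate poor tolerability from a change of supply. The SAP gives it no such role: Section 7.2 says it is meant to flag treatments taken after stopping. Reasons for discontinuation are recorded in the eCRF, and adverse events leading to discontinuation have their own table.

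**Conclusion.** The point holds in a limited form. The imputation rule and the class definitions together give a wrong class to a commercial nintedanib start that follows the last trial dose when its recorded date is partial and shares that dose's month, or its year if the month is missing. The post-discontinuation summary can then undercount, and the on-treatment table, not the new summary, can show apparent double use.

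A reader might go further and say that the summary does undercount. The documents do not support that, because the fraction of partial dates is unknown and with complete dates there is no error. Assuming uniform last-dose dates and gaps spread over days 1 to 28, the loss is about half the fraction of day-missing dates; it is larger if switches are prompt.

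Severity is minor. The affected outputs are descriptive concomitant-therapy tables; the adverse-event primary endpoint does not use this rule.

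**What to change.** Add to SAP 6.6.2: for a therapy coded as nintedanib whose partial start date is compatible with a start after last trial drug intake, impute the later of the first possible day and last trial drug intake + 1 day. Under this rule none of the true starts in days 1 to 28 is moved to on-treatment, against 52% of day-missing ones now (gap uniform over 1 to 28).

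The bound has a converse risk: a nintedanib record that truly began before the last trial dose in the same month would be classed as post-discontinuation. So report the number of start dates imputed, and query these dates at the site where that is still possible.

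State in SAP 7.2 that a therapy started on the day of last intake belongs to one class only, and name the class.

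The cost is a few sentences in the SAP and a small programming change, with no new data collection.

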## 6.7 BASELINE, TIME WINDOWS AND CALCULATED VISITS

As a general rule, last available assessment before first trial drug intake will be used as baseline in 1199.33. If no assessment is available at visit 2, visit 1 will be used as baseline in 1199.33.

A windowing will be performed for all endpoints as described in [Table 6.7: 1](#), in order to assign data to the relevant study visit based on the actual day of the assessment. Data will be analyzed using the re-calculated visits in the statistical tables. However, in the listings, all visits performed will be displayed (even if outside time-window), along with the re-calculated visit. No time-windowing will be performed for the follow-up visit.

Table 6.7: 1 Time windowing rules for spirometry, physical exam, vital signs, pregnancy test

Time window of actual day 			Allocated to		
Start (S n ) day	End (included) (E n ) day	Length of the time-window [days]	Visit number (n)	Visit name	Planned day of the visit (V n )
1	1	1	1 or 2 	Baseline	1
2	22	21	3	2 weeks	15
23	36	14	4	4 weeks	29
37	64	28	5	6 weeks	43
65	127	63	6	12 weeks	85
128	211	84	7	24 weeks	169
212	295	84	8	36 weeks	253
296	393	98	9	48 weeks	337
394	$V_p + (V_{p+1} - V_p)/2 = 505$	$E_p - S_p + 1$	10	64 weeks	449 (V p )
$V_p + 1 + (V_{p+1} - V_p)/2$	$V_{p+1} + (V_{p+2} - V_{p+1})/2$	$E_{p+1} - S_{p+1} + 1$	11	80 weeks	561 (V p+1 )

Table 6.7: 1 Time windowing rules for spirometry, physical exam, vital signs, pregnancy test (cont'd)

...	...	...	...	Every 16 weeks thereafter	V p+2
...	...	...	...	...	V p+...

[1] First trial drug intake date is taken into account as a reference to calculate time windows [2] Depending on the last assessment before first trial drug intake (included), refer to [Section 6.7](#) for baseline definition

Table 6.7: 2 Time windowing rules for laboratory measurements

Time window of actual day 			Allocated to		
Start (S n ) day	End (included) (E n ) day	Length of the time-window [days]	Visit number	Visit name	Planned day of the visit (V n )
1	1	1	1 or 2 	Baseline	1
2	22	21	3	2 weeks	15
23	36	14	4	4 weeks	29
37	64	28	5	6 weeks	43
65	106	42	6	12 weeks	85
107	148	42	6a	18 weeks	127
149	190	42	7	24 weeks	169
191	232	42	7a	30 weeks	211
233	274	42	8	36 weeks	253
275	316	42	8a	42 weeks	295
317	365	49	9	48 weeks	337

Table 6.7: 2 Time windowing rules for laboratory measurements (cont'd)

366	421	56	9a	56 weeks	393
422	$V_p + (V_{p+1}-V_p)/2$ = 477	$E_p-S_p + 1$	10	64 weeks	449 ( $V_p$ )
$V_p + 1 + (V_{p+1}-V_p)/2$	$V_{p+1} + (V_{p+2}-V_{p+1})/2$	$E_{p+1}-S_{p+1} + 1$	10a	72 weeks	505 ( $V_{p+1}$ )
...	...	...	...	Every 16 weeks thereafter	$V_{p+2}$
...	...	...	...	...	$V_{p+...}$

[1] First trial drug intake date is taken into account as a reference to calculate time windows [2] Depending on the last assessment before first trial drug intake (included), refer to [Section 6.7](#) for baseline definition

For all endpoints, if two post-baseline visits fall in the same time interval after windowing has been applied, the measurement closest to the planned visit will be taken into account. In case two measurements are equidistant from the planned visit, then the last one will be picked.

If after windowing of visits at baseline, two values fall within the same baseline interval, then the last value will be taken into account.

The same rules will be applied for laboratory measurements.

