1. Visit 1 and Visit 2 may occur on the same date if the period between Visit 9 (End of Treatment) of the previous trial (1199.32 or 1199.34) and the first visit for 1199.33 is ≤ 6 weeks. This rule does not apply to patients requiring washout of bronchodilators, as they will need to sign informed consent at Visit 1 in order to be asked to perform washout for PFT at Visit 2.
2. Visit 1 should occur at least one day after the Follow-up Visit of the parent trial and Visit 2 within 12 weeks of Visit 9 (End of Treatment) of the parent trial (1199.32 or 1199.34).
3. The patient is required to sign informed consent prior to any study related activities.
4. For patients performing Visit 1 and Visit 2 on the same day, eligibility assessment will be based on laboratory data from Visit 9 of the parent trial. Laboratory tests, physical examination and vital signs will be performed only once on that day and will be recorded under Visit 2 in the eCRF.
5. Urine dipstick pregnancy tests will be provided by central lab and should be performed in all women of childbearing potential. If urine test is not acceptable to local authorities, a blood test can be done at a local laboratory.
6. An additional visit must be performed in case of dose reduction or increase. Please refer to [Section 6.2.4](#) for visit procedures.
7. Only medical conditions that are occurring concomitantly at the time of screening will be recorded as baseline conditions on the 1199.33 Remote Data Capture (RDC) system. This also applies to ongoing AEs from the parent trial at the time of screening. See ISF for further instructions.
8. Laboratory test only for liver function monitoring: AST, ALT and bilirubin. Blood may be collected at the investigational site, primary physician (GP or Pulmonologist) or external laboratory with specific study kits and sent to the central laboratory for analysis. Information, agreement and training of the primary physician or local laboratory will be ensured on an individual site basis.
9. Same scheme should be repeated as often as needed: one complete visit every 16 weeks and one intermediate visit for liver function monitoring.
10. End of Treatment Visit to be performed if a reason for withdrawal is met. Please refer to [Section 3.3.4](#).
11. A Follow-up (FU) Visit should be planned for 28 days after last drug intake (+7 days window).

Proprietary confidential information.

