4.2.1.2 Management of liver enzyme elevation

The guidelines for managing liver enzyme elevations are the same as is in the parent protocols. The following procedures are based on the *FDA Guidance for Industry. Drug-Induced Liver Injury: Premarketing Clinical Evaluation (P09-12413)*.

ALT or AST > 1.5 fold ULN and < 3 fold ULN

- Continue as planned

ALT or AST \geq 3 fold ULN and < 5 fold ULN with no signs of severe liver damage

- Reduce to 100 mg bid or interrupt treatment (to be decided by investigator, based on individual risk assessment)
- Re-test ALT and AST, as well as alkaline phosphatase, total bilirubin and eosinophils within 48 to 72 hours, then at approximately 7 days, then at approximately 2 weeks, and assess signs of severe liver damage:
 - If ALT and AST < 3 fold ULN after 2 weeks, return to initial dose if reduced, restart at reduced dose if interrupted. Monitor lab (see above) every 2 weeks for at least 8 weeks.
 - If ALT and/or AST \geq 3 fold ULN after 2 weeks or any time thereafter, permanently discontinue study medication.

ALT or AST \geq 5 fold ULN and < 8 fold ULN with no signs of severe liver damage

- Interrupt treatment.
- Re-test ALT and AST, as well as alkaline phosphatase, total bilirubin and eosinophils within 48 to 72 hours, then at approximately 7 days, then at approximately 2 weeks, and assess signs of severe liver damage:
 - If AST and ALT < 3 fold ULN after 2 weeks, restart at reduced dose. Monitor lab (see above) every week for 4 weeks, then every 2 weeks for at least 8 weeks.
 - If AST and/or ALT \geq 3 fold ULN after 2 weeks or any time thereafter, permanently discontinue study medication.

ALT or AST \geq 8 fold ULN or signs of severe liver damage

- Permanently discontinue study medication.

Proprietary confidential information.

© 2017 Boehringer Ingelheim International GmbH or one or more of its affiliated companies. All rights reserved.

This document may not - in full or in part - be passed on, reproduced, published or otherwise used without prior written permission.

- Patients showing these lab abnormalities need to be followed up according to [Section 10.1.1](#) of this clinical trial protocol and the “DILI checklist” provided in ISF.

Signs of severe liver damage are defined as:

Increase of liver transaminases (ALT or AST \geq 3 fold ULN) and:

- appearance of fatigue, nausea, vomiting, right upper abdominal quadrant pain or tenderness, fever, rash, and/or eosinophilia ($>$ 5%); or

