5.3.3 Safety laboratory parameters

The laboratory tests will include:

- Haematology: red blood cell count, haemoglobin, haematocrit, mean corpuscular volume, white blood cell count including differential, platelet count.
- Chemistry: creatinine, AST, ALT, total protein, alkaline phosphatase, total bilirubin.
- Coagulation: International normalized ratio (INR) and partial thromboplastin time (PTT).

If laboratory values indicate toxicity, adequate and more frequent blood sampling will be performed at the discretion of the investigator.

Laboratory analysis during main visits will be done using central laboratory services. Venous whole blood will be collected in appropriate syringes provided by the sponsor through the assigned central laboratory. Details regarding centrifuge, processing, storage and shipment of samples will be determined by the central laboratory in accordance with the sponsor. The investigators will be informed and instructed by the central laboratory and detailed documentation will be included in the ISF.

Additionally, all patients will have intermediate liver function monitoring visits (AST, ALT and bilirubin) when the interval between 2 regular visits exceeds 8 weeks. At these visits blood may be collected at the investigational site, primary physician (GP or Pulmonologist) or external laboratory. However analysis will still be performed by the central laboratory.

In case of liver enzymes elevation, close monitoring must be ensured by the investigator (please refer to [Section 4.2.1.2](#)).

For patients continuing treatment with nintedanib within this trial after the database lock for the final analysis, laboratory tests will no longer be part of the trial related procedures. However investigators are encouraged to monitor liver function locally according to the recommendations provided in the Investigators Brochure and to manage liver enzyme elevations according to the recommendations provided in [section 4.2.1.2](#) Management of liver enzyme elevations.

Proprietary confidential information.

© 2017 Boehringer Ingelheim International GmbH or one or more of its affiliated companies. All rights reserved.

This document may not - in full or in part - be passed on, reproduced, published or otherwise used without prior written permission.

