6.2.2 Treatment period

If the patient has been determined eligible by the investigator to enter the trial (refer to [Section 3.3](#)), the investigator will assign a medication number to the patient through IVRS/IWRS at Visit 2 (refer to [Section 4.1.2](#)). First dose of nintedanib will be administered at Visit 2 in the clinic (day 1).

Additional clinic visits will be scheduled after 2, 4, 6, 12, 24, 36 and 48 weeks of treatment (Visits 3-9). Liver function monitoring visits will be performed at 18, 30 and 42 weeks of treatment (Visits 6a, 7a and 8a). After the first year of treatment, complete clinic visits will be scheduled every 16 weeks with intermediate liver function monitoring visits.

For detailed description of the trial procedures at each visit and dispensing schedule, please refer to the [Flow Chart](#).

End of Treatment (EOT)

If a reason for drug discontinuation is met (refer to [Section 3.3.4](#)) an EOT Visit should be scheduled as soon as possible after last drug intake. Reason for discontinuation must be documented in the eCRF.

For detailed description of the trial procedures at the EOT visit, please refer to the Flow Chart.

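### SAP Table 6.7: 2 gives all laboratory parameters the intermediate-visit windows, where only AST, ALT and bilirubin are scheduled, so such rows for other parameters would be largely selected on outcome

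*SAP*

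**What the plan says.** **Protocol, sampling.** Flow Chart footnote 8, attached to the laboratory row at visits 6a, 7a, 8a and Xa, reads: "Laboratory test only for liver function monitoring: AST, ALT and bilirubin". Section 5.3.3 agrees: "Additionally, all patients will have intermediate liver function monitoring visits (AST, ALT and bilirubin) when the interval between 2 regular visits exceeds 8 weeks". The full panel is drawn at the clinic visits and at EOT. It contains haematology, INR, PTT and the item "Chemistry: creatinine, AST, ALT, total protein, alkaline phosphatase, total bilirubin". No laboratory test is scheduled at the follow-up visit, and none is listed for the dose modification visit (Section 6.2.4).

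**Protocol, unscheduled samples.** Section 5.3.3 lets the investigator sample more often if values indicate toxicity. Section 4.2.1.2 adds, for ALT or AST at 3 to below 8 fold ULN: "Re-test ALT and AST, as well as alkaline phosphatase, total bilirubin and eosinophils within 48 to 72 hours".

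**SAP, windows.** Section 6.7 has two window tables. Table 6.7: 1 (spirometry, physical examination, vital signs, pregnancy test) has clinic-visit rows only. The second, "Table 6.7: 2 Time windowing rules for laboratory measurements", adds rows for the intermediate visits and makes no distinction by parameter. The section also states: "Data will be analyzed using the re-calculated visits in the statistical tables". Only the follow-up visit is exempt, so EOT samples are windowed. If two values share a window, the one nearer the planned day is kept.

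**The concern.** A by-visit table is normally read as a time course of the treated cohort. Under the rule as written, a haemoglobin or creatinine table could run week 12, week 18, week 24, with weeks 12 and 24 describing nearly everyone still on drug. Week 18 would describe a small group who were stopping drug, being worked up for toxicity, or far off schedule. A mean or change from baseline in that row reflects who was sampled as much as any drug effect. Long-term safety is the sole stated objective, and the laboratory time course is part of how it is described. The pattern would recur at weeks 30, 42, 56, 72 and later.

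**Working it through.** **1. Reproduce the plan's windows.** Each window ends midway between planned days: E(n) = V(n) + [V(n+1) − V(n)]/2. For visit 6: 85 + (127 − 85)/2 = 106. For visit 6a: 127 + (169 − 127)/2 = 148. For visit 10: 449 + (505 − 449)/2 = 477. Every end day stated in Table 6.7: 2 reproduces. Those of Table 6.7: 1 from visit 6 on (127, 211, 295, 393, 505) also reproduce, as midpoints between clinic visits.

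**2. Can an on-schedule full panel land in an intermediate row?** The inputs are the Flow Chart tolerances (±3, ±7 or ±14 days) and the Table 6.7: 2 windows.

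| Clinic visit | Allowed days | Its window | Late days beyond tolerance needed to reach the next intermediate row |
|---|---|---|---|
| 6 | 82–88 | 65–106 | 107 − 88 = 19 |
| 7 | 162–176 | 149–190 | 191 − 176 = 15 |
| 8 | 246–260 | 233–274 | 275 − 260 = 15 |
| 9 | 330–344 | 317–365 | 366 − 344 = 22 |
| 10 | 435–463 | 422–477 | 478 − 463 = 15 |

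In the early direction the gap is 14 days; for visit 7, for example, 162 − 148 = 14. So no on-schedule full panel reaches an intermediate row. A clinic visit has to be at least 14 to 22 days outside its tolerance. What remains is EOT panels and toxicity-driven samples.

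**3. A case without any deviation.** EOT falls on day 130. Weight and vital signs go to week 24 (Table 6.7: 1, days 128–211). Haemoglobin from the same visit goes to week 18 (Table 6.7: 2, days 107–148), where haemoglobin is not scheduled.

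**4. Share of time covered by intermediate windows.**
- Days 65–365: 3 × 42 = 126 of 301 days, or 42%.
- Days 2–365: 126 of 364 days, or 35%.
- Each later 16-week cycle: 56 of 112 days, or 50%. Beyond visit 10a this assumes that clinic and intermediate rows keep alternating every 8 weeks, as the protocol's scheme does. The table's closing label says every 16 weeks.

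**5. Illustration for week 18 (days 107–148).** Assumptions: 750 patients (Protocol Section 3.1); constant drop-out at a phase II discontinuation rate p per 52 weeks (Section 1.2); every discontinuation gives an EOT panel. With h = −ln(1 − p)/364,

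N = 750 × exp(−106h) × [1 − exp(−42h)].

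| p | h per day | N |
|---|---|---|
| 16.3% | 0.000489 | 14.5 |
| 26.2% | 0.000835 | 23.6 |
| 37.6% | 0.001296 | 34.6 |

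At 26.2%, the patients still on drug number 750 × exp(−85h) ≈ 699 at day 85 and 750 × exp(−169h) ≈ 651 at day 169.

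**6. Where those EOT panels would go under Table 6.7: 1.** At 26.2%, days 107–127 hold 750 × exp(−106h) × [1 − exp(−21h)] ≈ 12 panels, and days 128–148 the other 12 or so. The first group falls in the visit 6 window, where a sample near day 85 usually exists and is kept instead. The second group would enter the week-24 row, about 12/651 = 1.8% of it.

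**The case against.** The strongest reply has five parts.

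- **The output is not specified.** SAP Section 7.8.2 names specific tables only for liver enzymes and bilirubin. The rest follows a sponsor laboratory standard that is not available, and parts of the SAP are removed. An exclusion elsewhere cannot be ruled out. This stands as a limit, but none is visible, and Section 6.7 as written sends all laboratory data to these rows.
- **Scheduled data are untouched.** This stands. A reader might infer that 42% to 50% of all laboratory values are misplaced. Step 2 shows otherwise: the shares concern only EOT and unscheduled samples.
- **The current rule keeps values at the time they were drawn.** A panel on day 127 is exactly week 18, whereas Table 6.7: 1 would label it week 12 or drop it. A reader might infer that clinic rows lose EOT values that belong to them; step 6 does not support this for about half of them. The reply therefore weighs against changing the windows alone, and the fix has to allow for it.
- **N is displayed.** A row of 24 beside rows of 650 would look sparse. But N does not tell the reader that the row consists of patients stopping drug or under work-up.
- **The illustration is an upper figure for EOT panels.** Patients who die or are lost may give none, and the phase II rates come from patients who had not already completed 52 weeks. This stands. Nor would the row be purely EOT: toxicity repeats, notably of alkaline phosphatase and eosinophils, and off-schedule visits can add to it.

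**Conclusion.** The point holds within narrow bounds. The SAP applies intermediate-visit windows to parameters not scheduled there, so any such row is a pseudo-visit filled by EOT, toxicity-driven or far off-schedule samples. Under the stated assumptions, up to about 24 EOT panels (range about 15 to 35) would form most of the week-18 row for a parameter such as haemoglobin. The documents give no rate for the other sample types.

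A reader might go further and infer that the trial's safety conclusions are at risk. The documents do not support that. The primary endpoint is adverse event incidence and uses no visit windows. AST, ALT and bilirubin are scheduled at these visits and windowed suitably. Time to first liver enzyme elevation and individual maximum elevations do not depend on visit windows. What is affected is the descriptive by-visit laboratory tables for the other parameters.

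**What to change.** In SAP Section 6.7:

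1. Restrict Table 6.7: 2 to AST, ALT and bilirubin.
2. Use the Table 6.7: 1 clinic-visit windows for all other laboratory parameters.
3. Show the EOT or last on-treatment value in a separate row, because the closest-to-planned rule would otherwise drop some EOT panels, for example most of those on days 107–127.
4. Keep unscheduled toxicity samples in listings and worst-value tables.

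If the sponsor's laboratory standard already does this, a sentence in Section 6.7 saying so is enough. The cost is a parameter-specific derivation and one extra table row. No new data are needed.
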